***Caloric Vestibular Stimulation
to Treat Symptoms Associated
with Parkinson's Disease.***

NCT02703844

July 25, 2018

Study Protocol Version #9a.

**Caloric Vestibular Stimulation to Treat Symptoms Associated with
Parkinson's Disease.**

Chief Investigator Contact Details:

[name]

*School of Psychology, University of Kent,
[name].*

1: *Abstract pg.3*

2: *Background pg. 3*

3: *Preparation of the Intervention pg. 7*

4: *Study Design pg. 9*

5: *Study Participants pg. 12*

6: *Analysis pg. 13*

7: *Deliverability pg. 14*

8: *Physical Infrastructure pg. 15*

9: *Study Management pg. 15*

10: *Schedule of Events and Procedures pg. 20*

11: *Cited Articles Pg. 21*

1. Abstract

Applicant Details

Lead Applicant: [name]

Co-applicants: [name], [name], [name]

Parkinson's Disease (PD) is a nationwide public health problem, inflicting a complex constellation of physical and neuropsychiatric symptoms which are shown to progress with time. This research will investigate the potential of caloric vestibular stimulation (CVS), a non-invasive form of brain stimulation, as a treatment for individuals who suffer from Parkinson's Disease. CVS works by cooling or warming the external ear canal which in turn activates the vestibular (aka balance) organs, fooling the brain into reacting as if a real head movement has occurred. Corresponding metabolic changes linked to plastic change and recovery are subsequently elicited across many brain areas. CVS can be administered without any technical expertise or supervision, so is suitable for home-based use.

We plan to recruit a diverse sample of 32 patients with idiopathic Parkinson's disease from outpatient NHS settings across South East England. We will investigate whether core cognitive and physiological deficits are responsive to stimulation by comparing participants' performance on behavioural and physiological measures after baseline and either active or placebo stimulation phases with the aim of drawing initial insights into the application of CVS within this population. The study design is based on a single-case study that recently demonstrated durable, clinically meaningful gains in the motor and cognitive symptoms of PD.

Project Duration

12 months

2. Background

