2.4 Overview of the Design Study

To investigate the impact of CVS on PD, a diverse sample of 32 individuals diagnosed with Parkinson's disease from community and outpatient settings will be recruited and will have an equal chance of receiving active or placebo stimulation.

Participants will first complete an initial 4 week period of baseline assessment to quantify their deficits and isolate any improvements due to natural recovery. Next the participants will be divided; one group will proceed to a phase of active stimulation where they will undergo two twenty minute sessions of CVS each day. In order to control for placebo effects, the other group will receive sham stimulation where two 20 minute sessions of inactive stimulation will be given each day.

Participants will complete a battery of physiological and behavioural assessments at the end of every four weeks to monitor their progress on the core symptoms of interest. At the end of the study all participants will re-do the full baseline assessment to determine whether any of their symptoms have responded to the stimulation. Participants will undergo an EEG test at baseline and then at the end of the study protocol to assess changes at the neuro-physiological level. Additionally, all patients will be subject to a short video recording at baseline and at the end of the protocol to provide qualitative evidence to clinical audiences and potential funders post-study.

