4.2 Study Schedule

Potential participants will be identified by the key clinician. If the individual fulfils the entry criteria, he or she will be approached by the key clinician who will inform him or her of the aims and nature of the study. If the patient wishes to receive further information then the clinician will inform the team of key researchers, one of who will meet with them to discuss the study in detail and provide them with an information and consent sheet. The individual will have 24-48 hours to decide whether they would like to participate. Where a favourable view is given, the trial will commence approximately 1 week later at the same location. Upon study registration idiopathic participants will be randomly allocated to one of two treatment arms (see below) with a ratio of 1:1 (cohort 1: cohort 2) (see figure 2). Randomisation of condition allocation will be carried out using an online randomizer (www.randomizer.org).

All participants (n= 32) will complete an initial baseline assessment encompassing a range of behavioural and functional skills (executive function, memory, perception, pain, rehabilitative

progress). Physiological functioning will also be captured using EEG/ERP. This baseline will take place during the first week of enrolment and will then be repeated again during week 4 in order to measure the rate of any spontaneous recovery. We will also perform a video recording of mobility and any other assessments that show impairment at baseline and at the end of the study protocol for comparative reasons.

Cohort one (n=16) will then proceed to the active phase of stimulation whereby CVS will be administered by a staff member or carer (depending on their circumstance) twice a day for 20 minutes, 7 days a week. The CVS device will be pre-set to fluctuate between cold (17°) and warm temperatures (42°) thereby activating the vestibular system. Cohort two (n=16) will instead complete a placebo arm for the duration of the study protocol. During this phase the CVS device will be fitted as normal but the earpieces will remain unpowered, which does not activate the vestibular structures.

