5.2 Sample Size and Anticipated Effect

We will recruit individuals receiving PD care from the West or East Kent Neuro-rehabilitation, psychiatry, or allied services referred to study by the participating clinicians, Drs [name], and [name]. Using the attached flyer, we will also advertise for participants through the local branch of *Parkinson's UK* – participants from our previous pilot were successfully recruited through this means. The flyer will be distributed via the local branch's email list and also posted on their website.

For all study participants, a letter will be sent to their GP informing him/her of his/her patients' involvement.

As this is a pilot study aiming to establish potential effect sizes that in turn will power a subsequent, more definitive efficacy study, no formal sample size calculation has been performed, however, comparable intervention studies in the literature report statistically significant effects with sample sizes of this magnitude. We estimate a total of 40 participants will be recruited with the expectation that 32 patients and their carers will comply with both the intervention and follow-up.

6. Analysis

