***Caloric Vestibular Stimulation in
Parkinson's Disease***

NCT02703844

July 25, 2018

Statistical Analysis Plan (SAP)

Caloric Vestibular Stimulation to Treat Symptoms Associated with Parkinson's Disease

Prepared by: [name], Senior Statistician,
Centre for Health Service Studies
University of Kent

Final Version: 10 August 2017

Amended: 15 August 2018

Investigator: [name]

Sponsor: [name]

Signatures for approval of SAP

Prepared by Trial Statistician: [name] (University of Kent)

Signature:

Date:

Reviewed and approved by:

Principal Investigator: [name]

Signature:

Date:

1. Research question

Do repeated sessions of caloric vestibular stimulation (CVS) induce durable, potentially clinically meaningful improvements in the persistent and disabling motor and non-motor symptoms of Parkinson's disease?

2. Study design

This is a prospective single-blind randomised parallel group pilot study. The study was designed to recruit a diverse sample of 32 individuals diagnosed with idiopathic Parkinson's disease from community and outpatient settings. Participants will be individually randomised to active and placebo arms.

Diagnosis	Treatment (2 x 20 mins sessions per day for 8 weeks)	Number of patients (N)
Idiopathic	Active stimulation (cohort 1)	16
	Placebo (cohort 2)	16

Randomisation will be conducted using online randomisation software (www.randomiser.org). All participants will be blinded to the treatment being administered.

Prior to the treatment phase of the study, there will be a 4 week baseline phase to measure the rate of natural and spontaneous recovery. Outcome measures will be recorded at week 1 and week 4, and after the beginning of the treatment phase, every 4 weeks until the end of the study.

3. Outcome measures

The primary assessment time will be 12 weeks follow-up and the following outcome measures will be analysed:

- Non-motor symptom scale total score (NMSS)
- MDS-UPDRS 1 (Non-motor aspects of experiences of daily living)
- MDS-UPDRS 2 (Motor aspects of experiences of daily living)
- MDS-UPDRS 3 (Motor Examination)
- MDS-UPDRS 4 (Motor complications)
- MDS-UPDRS total score
- PD-39 total score
- Hospital Anxiety and Depression scale (HADS)
 - Depression total
 - Anxiety total
- Epworth sleepiness scale
- Fatigue severity scale
- Montreal Cognitive exam
- Timed up and go

4. Sample size

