The sample size of 32 participants is based on recommendations by Brown¹ and Lancaster et al² as a minimum sample size required to estimate the variance of outcome measures to inform the design of a subsequent multi-site randomized control effectiveness trial. Based on previous studies, the expected dropout at 12 weeks was estimated as 20% and a total sample of 40 participants is planned to allow for dropout during the treatment and follow-up phase of the study.

5. Description of the dataset used for the analysis

An Excel database of study data will be created by [name]. This will contain a separate sheet for each outcome measure and will include baseline data, participant information (demographic and randomisation details, medical history including time since diagnosis, time on levodopa and use of other medications), outcome measures, treatment and visit dates and compliance data.

Data will be reformatted and imported from the excel database to SAS datasets prior to Statistical Analysis, using the SAS IMPORT procedure.

6. Statistical methods

Composite scores of the individual items of each measure will be calculated. Changes from baseline (average of two baseline measures at week 1 and week 4) will be calculated from the composite scores for statistical analysis.

Outcomes will be analysed using analysis of covariance (ANCOVA) to compare the change in the mean response across treatment groups. The outcomes will be adjusted for baseline by including the baseline measure (average of week 1 and 4) as a covariate.

Diagnostic tests and plots to assess the assumptions of normality will be performed prior to analysis. In the case of non-normality, equivalent non-parametric approaches will be utilised, or where appropriate, the data will be transformed prior to analysis.

The primary analysis will be intention to treat, including all available data for participants enrolled in the study. Non-compliance will be reported as an outcome for each group, and the level of missing data will be reported. Sensitivity analysis may be performed to assess the impact of missing data.

¹ Brown, R. (1995). On the use of a pilot sample for sample size determination. *Stat Med* 14, pp1933-1940.

² Lancaster, G.A. et al. (2004). Design and analysis of pilot studies: recommendations for good practice. *J Eval Clin Practice* 19, pp307-312.

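### The protocol and SAP give both 32 and 40 as the number recruited; 32 should be labelled as the number expected with week-12 data and 40 as the number randomised

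*SAP*

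**What the plan says.** Two sets of figures appear.

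**32 at entry.**
- Protocol, Abstract: "We plan to recruit a diverse sample of 32 patients".
- Protocol 2.4 gives the number to be recruited as "a diverse sample of 32 individuals diagnosed with" Parkinson's disease.
- Protocol 4.2 randomises 1:1 at registration. It then says "All participants (n= 32) will complete an initial baseline assessment", in the first week of enrolment, and continues with "Cohort one (n=16) will then proceed to the active phase of stimulation" and "Cohort two (n=16) will instead complete a placebo arm".
- SAP section 2: "The study was designed to recruit a diverse sample of 32 individuals". Its arm table lists 16 active and 16 placebo as the number of patients.

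**40 at entry, 32 remaining.**
- Protocol 5.2: "We estimate a total of 40 participants will be recruited", with 32 expected to comply with both intervention and follow-up.
- SAP section 4 calls 32 the minimum needed to estimate the variance of the outcome measures, puts expected dropout at 12 weeks at 20%, and says "a total sample of 40 participants is planned to allow for dropout during the treatment and follow-up phase".

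Protocol 9.2B adds that discontinued subjects are replaced until a participant quotient is reached. Neither document gives that quotient a value.

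**The concern.** The same number, 32, serves both as the count entering the trial and as the count left after dropout. With 20% expected loss it cannot be both. SAP sections 2 and 4 disagree with each other within one short document, and protocol 4.2 disagrees with protocol 5.2.

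The SAP justifies the sample size by the precision of a variance estimate that will inform the next trial. A team that recruited to the figure in SAP section 2 or protocol 4.2 would expect to end below the minimum that SAP section 4 sets for that purpose. A team that recruited to SAP section 4 would end with arm sizes that do not match the SAP's own table. The replacement rule has no numerical target, so it cannot tell them which to follow.

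**Working it through.** **Inputs.** Minimum 32, dropout 20% at 12 weeks and planned total 40 (SAP section 4). 40 recruited and 32 expected to comply (protocol 5.2). 32 at first baseline, 16 and 16 by cohort, ratio 1:1 (protocol 4.2). 16 and 16 (SAP section 2 table).

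**Step 1: reproduce the plan's figure.** Total = minimum / (1 − dropout) = 32 / (1 − 0.20) = 40. This is exact. Protocol 5.2 implies the same loss: (40 − 32)/40 = 8/40 = 20%. The two sample-size passages therefore agree, and both use 32 as the number remaining.

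**Step 2: 40 enrolled.** 40 × 0.80 = 32 expected with week-12 data. Per arm: 20 × 0.80 = 16. This meets the stated minimum in expectation.

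**Step 3: 32 enrolled, no replacement.** 32 × 0.80 = 25.6 expected with week-12 data. Per arm: 16 × 0.80 = 12.8. The shortfall is 32 − 25.6 = 6.4, and 6.4/32 = 20%.

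**Step 4: what the shortfall would cost in precision.** These figures are unadjusted, with two arms and residual degrees of freedom n − 2.
- Upper 95% limit on an SD, as a multiple of its estimate, is √(df/χ²(0.025, df)). For 32 participants (df 30) it is 1.34. For 26 (df 24) it is 1.39, and for 25 (df 23) it is 1.40.
- 95% half-width for an arm difference, in SD units, is t × √(2/n per arm). For 16 per arm it is 0.72. For 12.8 per arm it is 0.82.

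**Step 5: chance of reaching 32.** This assumes that participants drop out independently at 20%, which the documents do not state. From 32 enrolled, the chance that all stay is 0.80³² = 0.0008. From 40 enrolled, the binomial chance that at least 32 stay is 0.59. Even under the plan, 32 is an expectation and not a guarantee.

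**Step 6: can 32 be read as completers throughout?** That reading fits protocol 5.2 and SAP section 4. It does not fit the Abstract or SAP section 2, which attach recruitment to 32, or protocol 2.4. It also does not fit protocol 4.2, which places 32 at the first baseline visit and 16 per cohort at the start of treatment. SAP section 4 places the dropout later, in the treatment and follow-up phase.

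**The case against.** The strongest reply is that the only two passages that justify the sample size agree on 40 recruited and 32 remaining, so no shortfall is planned. That stands. The 25.6 and the precision losses in step 4 apply only if enrolment stops at 32. The replacement rule in protocol 9.2B might also make good some or all of the loss. It does not remove the inconsistency, because the rule names no number.

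It is also fair to say that this is a pilot with no formal sample size calculation. No power claim depends on the figure, the analysis method is the same under either number, and the precision loss is modest. That limits the weight of the point. It remains more than a slip of the pen, because it concerns how many participants are to be randomised.

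A reader might infer three stronger things, none of which the documents support:
- **That the trial as planned misses its minimum.** It does not: 40 are planned. Nor is 32 enrolled itself below 32; only the number with week-12 data would be.
- **That participants 33 to 40 would have no place in the allocation.** The documents describe an online randomizer and a 1:1 ratio. They describe no fixed list of 16 and 16, block size or list length.
- **That completers would be reported as everyone randomised.** SAP section 6 makes the primary analysis intention to treat on all available data for participants enrolled, and has the level of missing data reported. Protocol 6.1 presents dropouts by group, 9.2C reports their number and reasons, and the 9.3 log counts those who consent and those who drop out. No passage fixes the denominator at 32.

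**Conclusion.** The inconsistency is real and should be corrected. The Abstract, protocol 2.4 and 4.2, and SAP section 2 put 32 at entry. Protocol 5.2 and SAP section 4 put 40 at entry and 32 after 20% loss. The participant quotient in protocol 9.2B does not decide between them.

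The consequence is conditional. If enrolment stopped at 32, discontinued subjects were not replaced and dropout ran at the SAP's 20%, about 25.6 participants would be expected to have week-12 data, 20% below the stated minimum. If 40 are enrolled as the sample-size sections intend, the expected number is 32 and there is no expected shortfall. The 20% rate is explicit only in SAP section 4; protocol 5.2 implies it through 32 of 40, and counts those who comply with intervention and follow-up instead of those with a week-12 score.

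**What to change.** Use one set of figures in the protocol's Abstract, 2.4, 4.2 and 5.2 and in SAP sections 2 and 4: 40 randomised (20 per arm), and 32 expected with week-12 data (16 per arm). In particular:
- Correct the SAP section 2 arm table to 20 and 20 randomised, with a second column for the 16 and 16 expected at week 12.
- In protocol 4.2, give the first-baseline and cohort numbers as those randomised.
- In protocol 5.2, define the 32 in the same terms as SAP section 4, so that compliance and availability of week-12 data are not confused.
- In protocol 9.2B, say which number the participant quotient means: the number randomised or the number with week-12 data.

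The cost is wording and one table. The plan of 40 stays, no patients are added beyond it, and the analysis methods in SAP section 6 do not change.

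### The SAP promises intention to treat with all available data, but its week-12 ANCOVA is an observed-case analysis that leaves out the expected 8 of 40 without a week-12 score

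*SAP*

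**What the plan says.** SAP section 6 describes the primary analysis set: "The primary analysis will be intention to treat, including all available data for participants enrolled in the study". The same section gives the model: "Outcomes will be analysed using analysis of covariance (ANCOVA) to compare the change in the mean response across treatment groups", adjusted by "including the baseline measure (average of week 1 and 4) as a covariate". SAP section 3 fixes the time: "The primary assessment time will be 12 weeks follow-up".

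No imputation, carry-forward rule or longitudinal model is named. Section 6 says that the level of missing data will be reported, and non-compliance by group. A sensitivity analysis for missing data is optional and has no stated method.

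On the amount of loss, SAP section 4 says that "the expected dropout at 12 weeks was estimated as 20" per cent, and plans 40 participants so that 32 remain. On visits, SAP section 2 has outcomes recorded at weeks 1 and 4 and, "after the beginning of the treatment phase, every 4 weeks until the end of the study".

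Three places in the protocol bear on this. Section 6.1 plans repeated-measures tests. Section 4.4 limits the interim and follow-up visits (weeks 8, 12 and 16) to a subset of the measures, without saying which. Section 9.2B replaces discontinued participants until the target number is reached.

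**The concern.** Change at week 12 does not exist for a participant without a week-12 score. A single-time ANCOVA adjusted only for baseline must leave that person out, and a week-8 score has no place in the model. The promise about the analysis set and the stated model therefore do not match. The only safeguard that could show the effect of the loss may never be run.

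If participants who do badly leave one arm more than the other, those still observed are not comparable between arms. Protocol section 5.2 says that the pilot is meant to supply effect sizes for a later, definitive trial, so a shift in the estimate would carry into that design.

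**Working it through.** **1. Reproduce the plan's figure.** Inputs from SAP section 4: 32 participants wanted, 20% dropout. Number to recruit = 32 / (1 − 0.20) = 40, as stated. Expected without a week-12 score = 0.20 × 40 = 8, or 4 per arm under 1:1 allocation. That leaves 16 per arm. The documents do not say how many of the 8 would have a week-8 score, so the range is 0 to 8.

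**2. Precision for scale.** Take the SD of change given baseline as 1. The SE of the arm difference is √(2/n): √(2/16) = 0.35 SD with 16 per arm, √(2/20) = 0.32 SD with 20 per arm.

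**3. When the observed-case ANCOVA is biased.** Assumptions, none from the documents: all loss occurs after week 8 (the upper case); dropout depends on the week-8 score through a logistic rule; the correlation *r* between week-8 and week-12 change, given baseline, is 0.3 to 0.85. If dropouts in one arm average *m* SD worse than their arm at week 8, then those retained average 0.20 × *m* / 0.80 better at week 8, and *r* times that at week 12. The bias is the difference in this shift between arms.

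- *Selective loss in the active arm only, odds of dropout × 2.7 per SD worse.* Integrating the rule over a normal distribution gives *m* = 0.69, so the shift at week 8 is 0.20 × 0.69 / 0.80 = 0.17. Times *r* = 0.5, 0.7 and 0.85, the bias is 0.09, 0.12 and 0.15 SD in favour of active. Simulating trials of 20 per arm with 4 lost per arm gives 0.09, 0.13 to 0.14, and 0.15 to 0.16 SD.
- *The same with a steeper rule (log-odds 1.5 per SD).* Here *m* = 0.91 and the shift is 0.20 × 0.91 / 0.80 = 0.23. The bias is 0.07, 0.11, 0.16 and 0.19 SD at *r* = 0.3, 0.5, 0.7 and 0.85.
- *Loss at random.* Bias 0.
- *Poor responders leave both arms alike, no true effect.* The shifts cancel; bias about 0 (0.02 SD or less in simulation).
- *One common rule (log-odds 1.5 per SD) and a true effect of 0.5 SD.* Dropout becomes 16% active and 24% placebo. The effect is understated by 0.03, 0.05, 0.06 and 0.08 SD at *r* = 0.3, 0.5, 0.7 and 0.85.

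**4. What the week-8 score adds.** A likelihood estimate that uses week 8 has bias of 0.01 SD or less in these cases. In the first case its empirical SE is 0.352, 0.343 and 0.329, against 0.360, 0.361 and 0.356 for the ANCOVA at *r* = 0.5, 0.7 and 0.85. That is 2% to 8% smaller. If only half the dropouts have a week-8 score, the gain roughly halves. The near-zero bias follows from the assumption that dropout depends only on the observed week-8 score.

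**The case against.** The SAP never says that it excludes withdrawals. It is silent on missing week-12 scores, and all available data can be read as available cases. It also commits to reporting missing data and non-compliance. This is fair, but reporting the amount of missing data does not correct for it, and the stated model still cannot use a week-8 score.

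Two stronger readings are tempting. The first is that this is a completers-only analysis. The documents do not support that: a participant who stops stimulation but is assessed at week 12 stays in, so observed cases is the accurate term. The second is that the result is biased whenever poor responders leave. Step 3 shows otherwise: the loss must act differently in the two arms. The documents give no dropout figure by arm. Only the active arm receives thermal stimulation (protocol section 3.1), but section 9.1 calls the usual vestibular symptoms mild and short-lived. Differential loss is possible, not shown.

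It can also be said that even the unfavourable case is under half of one SE in a pilot, that week-8 data may exist for only some outcomes, and that the proposed model cannot recover people lost before week 8. All three stand. They limit the size and reach of the point, but do not close the gap between the promise and the model.

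**Conclusion.** The point holds as a mismatch between the stated analysis set and the stated model. On the SAP's own figures, 8 of 40 participants are expected to fall outside the primary analysis, whether or not they were seen at week 8, and no missing-data analysis is guaranteed. That part rests on the text alone.

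The bias is conditional. It is about 0.09 to 0.16 SD in favour of active (up to 0.19 under the steeper rule) if selective loss occurs in the active arm alone and all of it after week 8. It is about 0 if loss is alike in both arms with no true effect, and 0.03 to 0.08 SD toward no effect if one rule meets a true effect of 0.5 SD. The correlations and dropout rules are assumptions. The change is worth making because it is cheap, gains some precision even when loss is random, and brings the SAP closer to the repeated-measures analysis in protocol section 6.1.

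**What to change.** In SAP section 6:

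- For outcomes measured at week 8, make the primary analysis a likelihood-based repeated-measures model with treatment, visit, treatment-by-visit, averaged baseline and baseline-by-visit. Report the week-12 arm contrast. Include every randomised participant with any post-baseline score. Keep the week-12 ANCOVA as a sensitivity analysis.
- For outcomes not measured at week 8, keep the ANCOVA and label it *observed cases at week 12*.
- List which outcomes are taken at week 8, since SAP section 2 and protocol section 4.4 differ on this.
- Make the missing-data sensitivity analysis mandatory and define it, with at least one missing-not-at-random scenario. The model does not correct loss that depends on unseen scores, and does not recover those lost before week 8.
- State how the replacement rule in protocol section 9.2B fits with intention to treat, so that replaced participants are not dropped from the analysis set.

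The cost is SAP wording and a few lines of SAS, with no new data. The downside is a few more covariance parameters to estimate in a small sample.

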3. Preparation of the Intervention

The temperature-variable earpieces are integrated into a padded headset that is worn by the participant. It is activated by a microprocessor-based control system that executes the pre-planned thermal waveforms and includes safety lockouts if a fault condition occurs during use. Stimulation protocols (active vs. sham) will be pre-programmed onto the devices for participants.

The control unit has a small touch screen which is easy to use. To begin stimulation, patients will have to click a green arrow and a tone will be emitted to indicate that it has begun. The screen will also switch to a stimulation mode, where a blue horizontal line will turn red as the stimulation is completed. Once complete, a tone will be emitted again. In case of malfunction, a command will appear on the screen and stimulation will be immediately discontinued. A log file specifying probe temperature at every 2 seconds can be downloaded to a PC after stimulation to confirm that the device has operated as expected and that the participant has actually undertaken the treatment. Given the portable nature of the stimulation device (and the EEG recording apparatus), all stimulation and data acquisition can be performed at bedside by the patient, a carer or therapist.

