An exploratory covariate analysis of the outcomes NMSS total score, MDS-UPDRS 2 and MDS-UPDRS 3 will be performed to explore the relationship with response and the interaction between treatment group and the covariates age, gender, time since diagnosis, disease severity, compliance, time on levodopa, and other medication use. A sensitivity analysis of these outcomes will be performed excluding participants who have dementia, to reflect the study population of the follow-on study.

Summary statistics of the outcome measures will be calculated and presented in tables. Summary level data will be presented graphically to illustrate the main findings from the statistical analysis. The brief statistical analysis report will include an overview of methods, including details of data transformations and information about missing data, a summary of the main findings from the statistical analysis and summary tables and plots to support these findings.

The data will be analysed using the SAS software package (version 9.2).

7. Planned start and end of analysis

- Start of analysis: 08/2017
- End of analysis: 09/2017

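### Compliance, which is observed only after randomisation, is listed with baseline covariates and tested for interaction with treatment, so that exploratory analysis is open to bias

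*SAP*

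**What the plan says.** SAP section 6 states that "An exploratory covariate analysis of the outcomes NMSS total score, MDS-UPDRS 2 and MDS-UPDRS 3 will be performed". The purpose is "to explore the relationship with response and the interaction between treatment group and the covariates age, gender", and the list continues with "time since diagnosis, disease severity, compliance, time on levodopa, and other medication use". Each covariate is therefore used in two ways: as a predictor of response and as a modifier of the treatment effect. Compliance appears in the middle of the list with nothing to set it apart.

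Earlier in the same section, "Non-compliance will be reported as an outcome for each group". The main analysis is separate: "The primary analysis will be intention to treat, including all available data for participants enrolled in the study". Its ANCOVA names only the baseline measure as a covariate.

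On timing, Protocol section 4.2 says: "Upon study registration idiopathic participants will be randomly allocated to one of two treatment arms". Treatment sessions start after the four-week baseline and run in weeks 4 to 12 (Protocol Annex 1). The SAP section 2 table gives the schedule as "2 x 20 mins sessions per day for 8 weeks". Protocol section 3 describes a device log, downloaded after stimulation, "to confirm that the device has operated as expected and that the participant has actually undertaken the treatment". Compliance therefore cannot be known until after randomisation.

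The SAP does not define the compliance measure and names no method for estimating the effect of actual use that keeps the randomised comparison.

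**The concern.** Randomisation balances the arms on what exists at allocation. It does not balance them on what participants do afterwards. If people who are doing poorly skip sessions, compliance carries information about outcome even when the device does nothing. Putting compliance in the model then compares selected subsets of the two arms.

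The documents give reasons why the selection could differ by arm:

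- Protocol section 9.1 expects vestibular activation to bring on dizziness, drowsiness and mild nausea, while section 3.1 leaves the placebo earpieces unpowered.
- A completed session is not the same exposure in the two arms, so one unit of compliance does not mean the same thing in each.
- Protocol section 9.2B lets participants who miss sessions be discontinued and replaced, which may truncate the compliance range.

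At stake is a false finding that those who used the device more gained more from it. Calling the analysis exploratory warns about multiplicity and imprecision. It does not remove confounding.

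**Working it through.** **Figures in the plan.** The SAP's recruitment figure reproduces, 32 / (1 − 0.20) = 40, but the point does not depend on it. Full use is 2 × 7 × 8 = 112 sessions. No significance level is stated, so two-sided 5% is assumed.

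**Model.** With Y the outcome, T the arm, X the baseline and C standardised compliance:

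Y = b0 + bT·T + bX·X + bC·C + bTC·(T × C) + error

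There is no true treatment effect and no true effect modification. Y has SD 1 and there are 16 per arm (SAP section 2). The baseline-outcome correlation of 0.7 is an assumption, as is every correlation r between compliance and outcome.

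**What drives each bias.** Let s be the slope of Y on C within an arm, given X.

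- Interaction: bTC is approximately s(active) − s(placebo). It is zero when the slopes are equal, whatever the mean compliance.
- Treatment effect adjusted for C without the interaction term, with a common slope: bias = s × (mean C in placebo − mean C in active).

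The slope depends on what r refers to:

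- C tracks the baseline-adjusted outcome: s = r × √(1 − 0.7²) = 0.714r. At r = 0.5, s = 0.357.
- C tracks the raw outcome: s = r(1 − 0.49) / (1 − 0.49r²). At r = 0.5, s = 0.255 / 0.8775 = 0.291.

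**Interaction false-positive rate** (6,000 simulated trials per setting; repeat runs differ by about a point):

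| r active / r placebo | C tracks baseline-adjusted outcome | C tracks raw outcome |
|---|---|---|
| equal (0, 0.3, 0.5 or 0.6 in both) | about 5% | about 5% |
| 0.5 / 0.3 | about 9% | about 7 to 8% |
| 0.3 / 0 | about 13% | about 8 to 9% |
| 0.5 / 0 | about 26% | about 17% |
| 0.6 / 0 | about 38% | about 22 to 23% |

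**Adjusted treatment effect**, r = 0.5 in both arms and active-arm compliance 0.5 SD lower: 0.357 × 0.5 = 0.179 SD, or 0.291 × 0.5 = 0.145 SD. Simulation agrees to within about 0.01, and the interaction stays near zero. If better outcome goes with more use, the error favours the active arm.

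**A second model as a check.** Here the change score has SD 1, and an unmeasured prognostic factor correlates 0.5 with it. Baseline is not in the model.

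- Compliance correlates 0.5 with that factor in the active arm only: expected false interaction 0.5 × 0.5 = 0.25 SD per SD of compliance, found in simulation. The test rejects in 10% of trials at N = 32 and 73% at N = 400, so the bias does not shrink with sample size.
- Compliance correlates 0.5 in both arms and is 0.5 SD lower in active: expected bias 0.25 × 0.5 = 0.125 SD (0.13 simulated). The test of the adjusted effect rejects in 6.3% at N = 32 and 25% at N = 400.

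**With compliance left out.** In this second model the mean treatment effect is within 0.005 SD of zero and rejection is 4.3% to 5.7% in every scenario. The planned interaction tests fall from 3 × 7 = 21 to 3 × 6 = 18.

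**The case against.** The best defence is that bias is possible but not shown. The symptoms caused by active stimulation point first to a difference in mean compliance. A mean difference alone leaves the interaction test at about 5%. A false interaction needs a different compliance-prognosis slope in each arm, and no passage establishes one. People who feel worse might skip sham sessions just as often, and Protocol section 9.1 describes the nausea as mild and the symptoms as usually gone within 5 to 10 minutes. All of this stands. It limits the claim to an analysis that is open to bias. It does not make the analysis safe, because nothing in the documents secures equal slopes or equal means.

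A reader might infer more than the documents support in four places:

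- *The SAP contradicts itself by using compliance as both outcome and covariate.* It does not. Reporting compliance by group and exploring its association with response are compatible; the difficulty is the causal reading of a treatment interaction.
- *Other medication use is also a post-randomisation variable.* SAP section 5 files it under medical history, apart from the compliance data, so the natural reading is a baseline value. One clarifying word is enough.
- *The compliance result will steer the next trial.* The pilot is meant to inform one, but no passage says this result will be used that way.
- *The main result is compromised.* The primary ANCOVA does not condition on compliance.

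**Conclusion.** The point holds as a risk of bias in one exploratory analysis. It would be too strong to say that the plan gives a biased treatment-by-compliance result: with the same compliance-outcome relation in both arms, the interaction test keeps its nominal 5%.

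Outside that case the error rate depends on assumptions that the documents do not settle. It is about 7 to 9% at correlations of 0.5 against 0.3. It is 8 to 38% when the active-arm correlation is 0.3 to 0.6 and the placebo correlation is zero. The 38% is the extreme of that range: it needs the strongest correlation considered, none in placebo, and compliance that tracks the baseline-adjusted outcome. Separately, equal correlations of 0.5 with active-arm compliance 0.5 SD lower bias the compliance-adjusted effect by about 0.14 to 0.18 SD.

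The correction is worth making because it is cheap and because more participants would not remove the bias. It is not a threat to the trial.

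**What to change.** In SAP section 6:

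1. Remove compliance from the covariate and interaction list.
2. State that the remaining covariates, including medication use, are baseline values.
3. Define compliance, for example logged sessions out of 112, and report it by arm as already planned.
4. If the effect of actual use is wanted, prespecify an exploratory estimate with randomised arm as the instrument: the intention-to-treat difference divided by the mean fraction of active sessions completed. Label it as a rescaled intention-to-treat effect per full use. It assumes that allocation acts only through sessions received and that benefit is proportional to sessions. At an assumed 80% completion it multiplies the difference by 1 / 0.8 = 1.25 and, treating that fraction as fixed, its standard error by the same factor, so it adds no evidence of efficacy.
5. Present any within-arm association between compliance and response as descriptive and non-causal.

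The cost is a few sentences and one calculation. The plan loses a direct test of whether the treatment effect varies with use, and the instrument-based estimate will be imprecise at this sample size.
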